- To investigate whether the results of the Nutri+ module are reproducible over time or whether time effects are present, with a correlation coefficient of ≥ 0.75 between two measurement points considered successful.
- To evaluate the Nutri+ module (dietary questionnaire) against the Compl-Eat 24-hour recall method. Specifically, we aim to examine whether the Nutri+ module can accurately classify at least 75% of individuals into three categories for the 21 product groups.
- To evaluate the visualization of the profile wheel by users of the Nutri+ module.

3 Study design

This is a longitudinal randomized study to evaluate the Nutri+ dietary intake module. The Nutri+ module can be completed by participants at home via an online portal; it is filled out only once and takes approximately 30 minutes to complete. As a reference method, Compl-Eat is used. This is an online 24-hour recall method developed by Wageningen University & Research (Meijboom et al., 2017). Participants in the study can complete this 24-hour recall themselves at home via a portal, recording everything they ate and drank in the previous 24 hours. Based on the submitted data, the Compl-Eat platform can determine for an individual how much and what was consumed at both the product group and individual product levels. Compl-Eat is completed by participants on four non-consecutive days—three weekdays and one weekend day (Saturday or Sunday)—to obtain an accurate representation of an individual's average intake. The 24-hour recalls are manually checked for completeness by a researcher afterwards.

A randomized cross-over design is used, in which one group of participants completes the Nutri+ module first, while the other group completes Compl-Eat first. The days on which participants complete

the Nutri+ questionnaire and the days on which Compl-Eat is completed are randomly selected. There is a minimum interval of 7 days between the Nutri+ module and the first or last day of Compl-Eat.

In addition, possible time effects in dietary recording and the reproducibility of the Nutri+ module results are examined. To this end, participants are invited again after three to six months to repeat the entire procedure of completing the Nutri+ module once and Compl-Eat four times. The first series of questionnaires is sent out in April; the second series begins in September.

See Figure 2 for a schematic overview of the study design.

[figure not shown]

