The second phase involves recruiting participants through social media campaigns and the completion of the Nutri+ module and Compl-Eat. Participants are recruited via social media advertisements, which link them to an online information sheet. After reading the information sheet, participants can provide online informed consent for participation in the study. They are then automatically directed to an online screening questionnaire (see inclusion and exclusion criteria). This screening questionnaire automatically assesses whether the individual meets the study's selection criteria. Candidates who do not meet the criteria are informed immediately. Candidates who do meet the criteria are directed to a baseline questionnaire to collect various baseline data (medication use, physical activity, adherence to any dietary or nutritional rules, and allergies or intolerances). Participants are then informed about the further study schedule and procedures.

The study uses a cross-over design, in which participants are randomly assigned to one of two sequences: starting with the Nutri+ module or starting with Compl-Eat. Participants who start with the Nutri+ module during the first series (autumn 2022) will start with Compl-Eat during the second series (spring 2023), and vice versa.

For all participants, the days on which the Nutri+ module and Compl-Eat must be completed are randomly selected. Both the Nutri+ module and Compl-Eat are completed at home using login credentials for the respective online platforms. Participants are not informed of the full schedule in advance to minimize potential influence on their dietary behavior. One day before a participant's first "assessment day," they are contacted by email by a researcher, requesting that they complete either the Nutri+ module or Compl-Eat the following day. Participants can respond to this email if the scheduled day does not fit their personal planning. In that case, the researcher reschedules the assessment day, and the participant is contacted again at a later time.

During the first series (autumn 2022), all participants complete Compl-Eat on four days within a two-week period and complete the Nutri+ module once. A minimum interval of seven days is maintained between completing Compl-Eat and the Nutri+ module to prevent interference between the methods.

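### The weekday/weekend mix of the recalls is set by completion day rather than by the day recalled, and the first Compl-Eat request can reach participants before the recalled period is over

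*Combined protocol and SAP*

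**What the plan says.** Section 3 (Study design) states that "Compl-Eat is completed by participants on four non-consecutive days", made up of "three weekdays and one weekend day (Saturday or Sunday", and gives the purpose as "to obtain an accurate representation of an individual's average intake". The same section describes the recall as participants "recording everything they ate and drank in the previous 24 hours".

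Section 5 (Second Phase) states that "the days on which the Nutri+ module and Compl-Eat must be completed are randomly selected" and that in the first series "all participants complete Compl-Eat on four days within a two-week period". On notice, it states that "Participants are not informed of the full schedule in advance to minimize potential influence on their dietary behavior". It then describes an email, sent one day before the first assessment day, "requesting that they complete either the Nutri+ module or Compl-Eat the following day". A participant for whom the day does not suit may ask for another. No rule is given for choosing the replacement day.

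Section 8 bases all Compl-Eat analyses on the average over the four assessment days of a series and states no weighting by day type. Section 2 sets the goal of the Nutri+ module at the level of the individual, with correct three-category classification of at least 75% of individuals as a sub-objective.

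**The concern.** The calendar rule applies to the day the participant logs in, whereas the data describe the period before. If that period is the preceding day, a Saturday login records Friday, a Sunday login records Saturday, and a Monday login, which the plan counts as a weekday, records Sunday. No section defines the mix by intake day, so the rule does not secure the mix it was written for.

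This matters for product groups whose intake differs at weekends; alcohol, snacks, fast food and desserts are plausible candidates. For these, a participant's four-day mean depends partly on which days were captured. That is error in the reference method, but in the agreement table and the correlations it would appear as disagreement with Nutri+.

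The email raises a second, smaller point of the same kind. Its timing is also tied to the completion day, so a participant starting with Compl-Eat can learn of the recall while still eating the food to be reported, or just before. That works against the protocol's own reason for withholding the schedule.

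**Working it through.** **Inputs from the documents.** Four completion days, no two consecutive, three on weekdays and one on a Saturday or Sunday (Section 3); a two-week period and random selection of days (Section 5); recall of the previous 24 hours (Section 3); average over the four days (Section 8).

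**Assumptions, not in the documents.** The recalled period is the preceding calendar day, the window is 14 days, and all admissible schedules are equally likely.

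**The plan's own figure.** By completion day, the weekend share is 1 of 4 = 25% for everyone.

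**Step 1: count the schedules.** Listing every admissible set of four days for each of the seven possible start days gives 1,242 schedules. Each completion day is moved back by one day, and Saturdays and Sundays are counted among the recalled days.

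| Weekend days recalled | Schedules | Share |
|---|---|---|
| 0 | 212 | 17.1% |
| 1 | 700 | 56.4% |
| 2 | 324 | 26.1% |
| 3 | 6 | 0.5% |

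Two or more: 330/1,242 = 26.6%. Not exactly one: 542/1,242 = 43.6%, ranging from 41.6% to 49.5% by start day. No weekend day: 14.3% to 20.3% by start day.

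The weekend login day drives the pattern. With a Saturday login, 212 of 621 schedules (34.1%) record no weekend intake. With a Sunday login none has zero, and 257 of 621 (41.4%) have two or more.

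Without the non-consecutive rule, the shares for 0/1/2/3 are 23.3%/46.7%/26.7%/3.3%, so 53.3% do not have exactly one.

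**Step 2: group average.** (700 × 1 + 324 × 2 + 6 × 3)/1,242 = 1,366/1,242 = 1.10 weekend days of 4, or 27.5%. A calendar week has 2/7 = 28.6%.

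**Step 3: effect on one participant's mean.** Let weekday intake be 1 and weekend intake r, with k weekend days recalled. The expected four-day mean is (4 − k + k·r)/4, and the calendar-week mean is (5 + 2r)/7. The documents give no value for r, so the values below are illustrations.

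| r | k = 0 | k = 1 | k = 2 |
|---|---|---|---|
| 1.5 (week mean 8/7 = 1.143) | 1/1.143: −12.5% | 1.125/1.143: −1.6% | 1.25/1.143: +9.4% |
| 2 (week mean 9/7 = 1.286) | 1/1.286: −22% | 1.25/1.286: −3% | 1.5/1.286: +17% |

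With r = 2 and the group average of 1.10 weekend days, the mean is (4 + 1.10)/4 = 1.275 against 1.286, or −0.8%. The error is spread between participants, with little shift of the group mean.

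**Step 4: the email.** This needs no arithmetic. The email goes out one day before the first assessment day. In the sequence that starts with Compl-Eat, that is the day to be recalled if the window is the preceding calendar day. With a rolling 24-hour window, it comes before or during the window. In the other sequence the first assessment is Nutri+, so the email does not announce a recall. Section 5 swaps the sequences in the second series, so each participant starts with Compl-Eat in one of the two series. If the email is repeated in the second series, one recall of each participant's eight is shown to be announced in this way. Notice for recalls 2 to 4 is not described.

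**The case against.** The strongest reply is that the weekend balance does not fail. The group share of 27.5% is closer to the calendar 28.6% than the 25% that an exact three-to-one intake mix would give, and more than half of the schedules still contain exactly one weekend intake day. This stands. A reader might infer that the reference is biased as a whole, and the calculation does not show that. For the same reason, the −3% for a participant with exactly one weekend day should not be counted as a separate weighting bias: it presumes the one-in-four mix that the rule does not deliver. What remains is variation between participants, and a correct group mean does not remove that from an individual classification.

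Second, the percentages depend on reading the previous 24 hours as the preceding calendar day. The wording also permits a rolling window, and no completion time is stated. A Saturday-evening recall would then cover mostly Saturday, and the shift would be smaller. This also stands, and is a reason to define the window.

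Third, a reader might infer that the protocol promises unannounced recalls and breaks that promise. It does not: it says only that the full schedule is withheld, and the email is specified for the first assessment day alone. Nor do the documents show that advance notice moves reported intake in a particular direction, or that rescheduling removes unusual days selectively. Both are possible, and neither is established.

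Finally, the effect on the 75% agreement target has not been quantified. That would need intake distributions and weekday–weekend differences that the documents do not give.

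**Conclusion.** The point holds in limited form. The rule in Section 3 and the random selection in Section 5 govern completion days, so the intake-day mix is uncontrolled. Under the calendar-day and equal-likelihood assumptions, about 44% of participant-series miss the intended mix, including about 1 in 6 with no weekend intake day. The consequence is added error in individual reference values for product groups with a weekday–weekend difference. It is sizeable for a participant with none or two weekend days if that difference is large, and negligible if there is no difference. Agreement and correlations with Nutri+ could suffer for reasons unrelated to Nutri+.

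The notice point is narrower. The day-before email undercuts the stated aim for the first recall of the Compl-Eat-first sequence, and the plan is silent on notice for the remaining recalls.

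**What to change.** - Define day type by the recalled day. A weekend recall is completed on Sunday or Monday, and weekday recalls on Tuesday to Saturday. Every participant then has exactly one weekend intake day of four.
- Fix the recall window as the preceding calendar day.
- Send each Compl-Eat request on the completion day, after the recalled day has ended, and state this for all four recalls.
- Replace a refused day with a newly drawn day of the same recalled type.

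If data are already collected, classify each recall by intake day and report how many participants have no weekend day. Add a sensitivity analysis of agreement and correlations among participants with both day types, either unweighted or with the mean taken as 5/7 × weekday mean + 2/7 × weekend mean.

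The cost is a change to the scheduling rule and the email timing, or one extra analysis. The downside is shorter notice, which may lead to a few more rescheduled days.

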After completing the first series (autumn 2022), participants are reminded that they will be contacted again in spring 2023 to complete the Nutri+ module and Compl-Eat. The same procedures are followed in spring 2023 as in autumn 2022.

Participants are also asked to complete an evaluation questionnaire regarding their experiences with completing the questionnaire and the visualization of the dietary profile wheel.

After data collection for the evaluation study is completed, the data are analyzed. Based on this analysis, recommendations will be made for adjusting the Nutri+ module (questionnaire, algorithms, and cut-off values) and for improving the visualization of the profile wheel.

Tabel 2: Overview timeline and investment for participants evaluation study

	How often and when	Total time investment
--	--------------------	-----------------------

Nutri+ module	1 time filling out autumn 2022 1 time filling out spring 2023	2 times, 20 minutes. 40 minutes in total.
Compl-eat	1 time 4 days filling out autumn 2022 1 time 4 days filling out spring 2023	80 minutes per time. 160 minutes in total.
Evaluation questionnaire	1 time filling out	15 minutes

6 Outcome variables

To evaluate the Nutri+ module in comparison with Compl-Eat, it is first necessary to assess the extent to which the food groups used in the Nutri+ module are also available in Compl-Eat. The outcomes listed below depend on the results of this mapping. In addition, Compl-Eat will need to apply the same food group classification based on the same cut-off values per product group as used in the Nutri+ module.

Primary outcomes

- Intake in grams for the 17 product groups that are quantitatively assessed (Fruit, Vegetables, Legumes, Nuts and Seeds, Fish, Dairy, Meat, Eggs, Soft Drinks, Alcohol, Coffee, Tea, Snacks, Sweet Spreads, Chips/Nuts/Party Snacks, Fast Food, Desserts/Ice Cream/Cakes) for both Compl-Eat and the Nutri+ module.

Secondary outcomes

- Evaluation overall and by subgroup (sex, BMI, etc.) for all product groups available in both Compl-Eat and the Nutri+ module, for which guidelines exist to assess reproducibility and classification. For Nutri+, these include: Fruit, Vegetables, Butter and Cooking/Frying Products, Dressings and Oils, Legumes, Nuts and Seeds, Fish, Dairy, Meat, Eggs, Cereal Products, Potatoes, Soft Drinks, Alcohol, Coffee, Tea, Snacks, Sweet Spreads, Chips/Nuts/Party Snacks, Fast Food, Desserts/Ice Cream/Cakes.
- Energy intake based on Compl-Eat

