- Expected energy intake based on sex, age, weight, and physical activity
- Evaluation of the profile wheel

7 Description of incidents, safety, adverse events, side effects

The study for participants consists of completing dietary questionnaires and 24-hour dietary recalls. Due to the nature of the study, no incidents or adverse events are expected. Any complaints regarding the conduct of the study, the websites used, or other questions or remarks can be submitted via email or telephone, as indicated in the participant information.

8 Data-analysis and statistics

For Compl-Eat, all analyses will be based on the average intake per product group across the four assessment days within a single measurement series (spring or autumn).

Based on the Compl-Eat data, it will be assessed whether there is excessive under- or over-reporting in the study population. To this end, the number of calories consumed, as calculated by Compl-Eat, will be compared with the expected caloric intake based on participants' age, sex, height, and weight.

The agreement between classifications in Compl-Eat and the Nutri+ module will be evaluated by assessing the percentage overlap in categorization and subsequently examining correlations between the scores. The goal is for 75% agreement per product group between the Nutri+ module and Compl-Eat. If lower agreement is observed, the data will be qualitatively examined to identify areas for improvement in the Nutri+ module.

In addition, the intake in grams per product group as measured by the Nutri+ module and Compl-Eat will be examined. Correlation coefficients will be calculated to assess agreement between the Nutri+ module and Compl-Eat. These outcomes are primarily exploratory and aim to provide insight into where the largest differences between Compl-Eat and Nutri+ occur. These insights can be used to further improve the Nutri+ module.

To assess the reproducibility of the Nutri+ module, correlations between the spring and autumn measurements will be used.

Participants' opinions on the visualization of the profile wheel will be evaluated using descriptive information.

9 Risk analysis relating to the conduct of the study

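### Nutri+ reproducibility should be estimated within randomised sequence: the order reversal puts eight recalls between the two completions in one sequence and none in the other

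*Combined protocol and SAP*

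**What the plan says.** Section 5 (Second Phase) states that "participants are randomly assigned to one of two sequences: starting with the Nutri+ module or starting with Compl-Eat". The order is then swapped for the second series: "Participants who start with the Nutri+ module during the first series (autumn 2022) will start with Compl-Eat during the second series (spring 2023", and the opposite for those who began with Compl-Eat.

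The content of a series is fixed. In Section 5, "all participants complete Compl-Eat on four days within a two-week period and complete the Nutri+ module once". In Section 3, "Compl-Eat is completed by participants on four non-consecutive days", made up of three weekdays and one weekend day, and "There is a minimum interval of 7 days between the Nutri+ module and the first or last day of Compl-Eat". For the second series Section 5 adds: "The same procedures are followed in spring 2023 as in autumn 2022".

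Section 2 makes reproducibility over time a sub-objective, "with a correlation coefficient of ≥ 0.75 between two measurement points considered successful". The whole analysis text for it in Section 8 is: "To assess the reproducibility of the Nutri+ module, correlations between the spring and autumn measurements will be used". Neither that sentence nor the subgroups named in Sections 4 and 6 mention randomised sequence, the number of recalls done between the two completions, or the actual retest interval.

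**The concern.** Reversing the order is a sensible way to balance the Nutri+ versus Compl-Eat comparison. The same reversal makes the retest comparison different in the two sequences. One group first fills in Nutri+ with no recall experience and fills it in again after eight detailed recalls. The other fills it in twice with four recalls behind it and none in between, after a shorter interval.

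Repeated recalls could change how people judge portions and frequencies. The plan allows for one method influencing the other, since Section 5 gives this as the reason for the 7-day gap. A 7-day gap may limit short-term carry-over, but it does not equalise eight recalls and none.

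At stake is the reading of a stated success threshold. A correlation over all participants describes neither retest condition. It can also be pulled down by a mean difference between sequences that has nothing to do with how consistently Nutri+ ranks people. The sub-objective also asks about time effects, and in the Nutri+-first sequence elapsed time and recall practice cannot be separated.

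**Working it through.** The plan gives no calculated figure to reproduce here: 0.75 is a threshold, and the 200 participants come without an expected correlation or a power statement. The check is therefore of structure, timing and possible size.

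**1. Recalls between the two Nutri+ completions** (order from Section 5; four recalls per series from Sections 3 and 5)

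- Nutri+ first: Nutri+, 4 recalls, months, 4 recalls, Nutri+. Between completions: 4 + 4 = 8. Before the first completion: 0.
- Compl-Eat first: 4 recalls, Nutri+, months, Nutri+, 4 recalls. Between completions: 0. Before the first completion: 4.

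**2. Retest interval** (two-week window from Section 5; 7-day minimum gap from Section 3)

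- Four non-consecutive days within 14 days span 6 to 13 days from first to last.
- Adding the 7-day gap, Nutri+ lies 7 + 6 = 13 to 7 + 13 = 20 days from the farthest recall in each series.
- With series starts S days apart, the Nutri+-first interval is S + 13 to S + 20, and the Compl-Eat-first interval is S − 13 to S − 20.
- Difference: 2 × 13 = 26 to 2 × 20 = 40 days. The result is the same if the months are counted from the end of series 1 to the start of series 2.
- Against three months (91 days) this is 26/91 = 29% to 40/91 = 44%. Against six months (182 days) it is 14% to 22%.

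Because 7 days is a minimum, 40 is not a ceiling: a 10-day gap gives 32 to 46 days. If series 2 were timed from each person's own Nutri+ date, which is not stated, the difference would be 13 to 20 days. Section 3 gives April then September, and Section 5 gives autumn 2022 then spring 2023. These must be reconciled, but neither the 8 versus 0 count nor the 26 to 40 days depends on them.

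**3. Effect on the pooled correlation** (assumed values)

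Take two equal sequences with unit variance within each, and a mean difference d between sequences at one of the two completions only. The covariance is unchanged and one variance is inflated by d²/4:

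r_pooled = [(r_A + r_B)/2] / √(1 + d²/4)

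- r_A = r_B = 0.75, d = 0.3: 0.75/√1.0225 = 0.742.
- r_A = r_B = 0.75, d = 0.5: 0.75/√1.0625 = 0.728.
- r_A = 0.70, r_B = 0.80, d = 0: 0.75. With 0.65 and 0.85, also 0.75. One pooled figure can hide a real split.

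For interval alone, assume exponential decay from 0.85 to 0.90 at zero interval to 0.75 in the Compl-Eat-first sequence. The mildest case is 0.75 × (0.75/0.85)^(26/182) = 0.74. The strongest is 0.75 × (0.75/0.90)^(40/91) = 0.69.

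**4. Precision by sequence** (Fisher z, 1:1 allocation assumed, no dropout)

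z(0.75) = 0.973, with standard error 1/√(n − 3).

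- 200 pooled: 0.973 ± 1.96/√197 gives 0.68 to 0.80.
- 100 in one sequence: 0.973 ± 1.96/√97 gives 0.65 to 0.82.
- Two sequences of 100 combined on the z scale: 0.973 ± 1.96/√(97 + 97) gives 0.68 to 0.81, almost the same as pooled.
- Power to detect a difference between sequences (two-sided 0.05, standard error √(2/97)): about 36% for 0.70 versus 0.80, and 92% for 0.65 versus 0.85.

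**The case against.** **Pooling is inferred.** Section 8 speaks of correlations in the plural and does not say pooled. That is fair. But the plural is naturally read as one per product group, and sequence is named neither there nor among the subgroups. As written, nothing separates the sequences.

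**The size is unknown and may be small.** This stands. The documents give no retest correlation and no practice effect. Four of the eight recalls lie months back, and the timing between series may vary by about three months anyway, so the interval part is probably modest. A reader might infer that the design will cause a false failure against 0.75. That needs assumed values for the true correlation and for the effect of recalls, so it is a possibility and not a finding. Section 8 also attaches no decision rule to missing 0.75, and results feed into improving the module.

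**The Compl-Eat-first sequence could serve as the clean retest.** A reader might want to rest the criterion on it alone. The documents do not support this. That sequence has the shorter interval, its participants have already done four recalls before either completion, and it would halve the sample. Its first completion can follow the recalls by 7 days and its second by months, so it is not an untouched retest either.

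**The order could be kept the same in both series.** This would put four recalls between completions for everyone, but at different distances from the second completion. It would also give up the within-person counterbalancing that serves the main objective. The documents do not call for it.

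**Some retests might seem to miss the three-to-six-month window.** Section 3 times the invitation to the second series. It states no Nutri+-to-Nutri+ window, so none is breached.

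**Conclusion.** The concern holds in a limited form. Eight versus zero intervening recalls follows directly from Sections 3 and 5. The 26 to 40 day difference follows at the tightest permitted schedule. Section 8 ignores both in the correlation that Section 2 judges against 0.75, so that coefficient mixes two retest conditions.

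The illustrated loss from 0.75 to 0.74 or 0.73 rests on an assumed mean difference of 0.3 to 0.5 SD at one completion, equal sequences and equal variances. A difference of the same sign at both completions could instead raise the pooled value. In either case it would not reflect consistency within persons. The reversal itself is a legitimate design choice; the gap is in the analysis. It is worth closing because the remedy uses data already planned and changes what the criterion can be said to show.

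**What to change.** In Section 8, specify that:

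- The Nutri+ reproducibility correlation is calculated within each randomised sequence, and both estimates are reported with 95% confidence intervals.
- The actual Nutri+-to-Nutri+ interval is summarised by sequence.
- The 0.75 criterion is judged on the sequence-stratified estimate, for example the within-sequence Fisher z values averaged with weights n − 3 and back-transformed. If a rank correlation is used, ranks are taken within sequence.
- The difference between sequences is descriptive, with no test-based conclusion.

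Stratification removes mean differences between sequences. It does not undo person-specific changes from recall practice or a longer interval within a sequence, which is why both estimates should be shown beside the combined one.

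The cost is a few sentences and some extra table rows. There are no new data, no change to the schedule or the order, and almost no loss of precision for the criterion (0.68 to 0.81 against 0.68 to 0.80 at r = 0.75). The separate estimates are wider, at about 0.65 to 0.82 each with 100 per sequence, and wider still if participants drop out before series 2.
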